#### Secondary endpoints/outcomes

Stimulated C-peptide <0.2nmol/L at 3 years ('absolute insulin deficiency') (27, 28)

C-peptide rate of change (UCPCR and plasma)

HbA1c (mean and at 3 years)

Weight change (baseline to 3 years)

Self-reported hypoglycaemia & hypoglycaemic awareness (29, 30)

Wellbeing and resilience (SF12 and CD-RISC questionnaire) (30, 31)

Ketoacidosis (self-reported and confirmed from medical notes)

This research will produce a robustly validated clinical prediction model that will for the first time integrate validated clinical features and biomarkers to allow clinicians to accurately assess classification and need for insulin treatment at diabetes diagnosis. The model will be freely available to clinicians and patients through a website and smartphone App.

#### 4. STUDY DESIGN

Prospective observational study. We will recruit a prospective cohort of 1200 adults diagnosed with diabetes within the previous 1 year and aged between 18 and 50 at the time of diagnosis.

We will also recruit an additional cohort of 800 participants diagnosed with diabetes in the last year aged >50 at diabetes diagnosis, with recruitment stratified by insulin treatment (400 insulin treated, 400 non insulin treated).

At baseline (visit 1) blood & urine samples will be collected for biomarker assessment and biobanking, and clinical features recorded. We will follow participants for 3 years with annual remote contact (phone, email or letter) and postal urine or capillary blood sample for C-peptide. A further face to face visit with blood & urine sampling will be performed at 3 years.

We will assess the utility of adding biomarkers to clinical features in diagnosing diabetes subtype (defined by insulin requirement at 3 years), and where utility is shown, integrate these into a probability model.

Please also refer to the study summary flow chart on page 7 for a summary of study procedures.

#### 4.1 STUDY SETTING

NHS primary care, secondary care, or community setting.

This is a multicentre study and participants will be recruited through up to 60 recruiting sites in the UK.

Recruiting sites will need to confirm the following capabilities in order to deliver the study:

- Ability to recruit (possibly with the assistance of PICs) at least 30 participants before 31 December 2019
- Sufficient research nurse time to undertake the recruitment and all follow-up procedures as detailed in the study design for the full duration of the study.
- Research nurse(s) must be trained and competent in phlebotomy.
- Ability to spin blood samples (in accordance with SOPs provided by the CI) and despatch on day of collection to the lead site in Exeter, UK.  
**Note:** Samples transferred to the Royal Devon and Exeter Hospital blood sciences laboratory for analysis will be labelled with participant identifiable data (Name, date of birth & NHS number) in accordance with the requirements for clinical sample analysis. Once initial analysis is complete, the remaining samples will be anonymised and assigned an individual study code prior to storage.
- Undertake to transfer scanned (PDF) copies of data collection forms, consent forms & biochemistry results (via secure nhs.net email) to the CI site within 5 working days of the study visit.

- Full contact details for both patients and clinicians (GP or secondary care) will have to be included in the information transferred to the lead site, to facilitate feedback of antibody results after visit 1 and C-Peptide result at 3 years.
- Undertake to transfer scanned (PDF) copies of recruitment logs and site specific delegation logs to the CI site on a monthly basis to facilitate remote site monitoring requirements.

## 4.2 ASSESSMENT AND MANAGEMENT OF RISK

### Concurrent medication and diabetes management:

This is an observational study therefore all decisions on patient management will continue to be taken by participant's usual clinicians. All diabetes medications will be unaltered.

### Blood sampling:

Blood samples will be taken which may result in slight pain and bruising. Samples will be taken by staff trained and experienced in venepuncture procedures.

### Patient burden:

Participation involves 2 blood samples (3 years apart) and 2 additional remote contacts (phone, email or letter according to participant preference) over the 3 year period. Participants will also collect a urine sample or capillary blood sample at home on 4 occasions.

### Concomitant studies:

Recruitment to this study does not preclude recruitment to concurrent studies related or unrelated to diabetes

### Reporting adverse events

This study is categorised as:

- Type A = No higher than the risk of standard medical care

This is a low risk study and it is not anticipated that participants involved in this project will be subject to adverse or serious adverse events (AEs/SAEs).

AEs/SAEs that occur as a result of study participation (e.g. venepuncture during research visit) should be reported to the study sponsor and CI, with 24 hours of notification, in accordance with the SAE/AE SOP and report forms provided to recruiting sites in their study site file. These study related AEs/SAEs should also be reported locally in accordance with individual Trust protocols.

AEs/SAEs that are not a result of study participation should be dealt with at each recruiting site in accordance with their local Trust protocols.

## 4.3 ELIGIBILITY CRITERIA

### 4.3.1 Inclusion criteria

- Adults diagnosed with diabetes within the previous 12 months.
- Aged  $\geq 18$  and  $\leq 50$  at the time of diabetes diagnosis or (additional late onset diabetes cohort) aged  $>50$  at the time of diabetes diagnosis\*.

- Able and willing to provide informed consent.

\* Clinical diagnosis of diabetes mellitus. Biochemical diagnosis confirmed from healthcare records post recruitment.

#### **4.3.2 Exclusion criteria**

- Gestational diabetes
- Known secondary diabetes (diabetes considered likely due to medication, cystic fibrosis, pancreatitis, pancreatic cancer, pancreatic surgery, hemochromatosis or Cushing's syndrome).

## **5 STUDY PROCEDURES**

Please refer to the flow chart on page 7 for a summary of the study procedures.

The study procedures described below will be conducted in accordance with detailed SOPs provided to all sites by the CI.

### **5.1 Identification & Recruitment**

#### **5.1.1 Patient Identification & Eligibility Screening**

Eligible participants will be identified in the following ways:

- At routine clinical care appointment (primary and secondary care): Clinicians will introduce the study to eligible patients and obtain verbal consent for the research team to contact the participant to discuss the study in more detail.
- Regular screening of primary and secondary care records: Clinicians will carry out periodic searches of their patient lists to identify eligible patients and invite those patients to take part in the study by letter, email, telephone or in person at the patient's next appointment.
- Retinal Screening: Invitation letter or copy of the study poster (advertisement) sent to new retinal screening participants.
- Self-referral: Study posters (advertisements) will be displayed in primary care, secondary care or community settings. The study may also be promoted on research websites & appropriate social media (e.g. diabetes or research specific Facebook pages) using wording from ethically approved study documents (ie patient information sheet or study poster)
- Identification from existing research databases where participants have given formal written consent for contact about further research.

This is a multicentre study and identification methods will vary by centre, for example it is likely some sites will recruit from only secondary or primary care

#### **5.1.2 Targeted recruitment of participants aged over 50 by insulin treatment status**

To ensure sufficient prevalence of the primary study outcome of Type 1 diabetes in those over age 50 recruitment of this age group will target equal numbers (400 each) of participants receiving insulin treatment at the time of recruitment (high prevalence Type 1), and those not receiving insulin treatment (low prevalence Type 1). This will be managed using separate recruitment targets for these subgroups, based on prior recruitment rate, with recruitment to the non insulin treated cohort limited to a subset of study sites.

### 5.1.3 Screening

A member of the research team will contact referred/identified patients directly to discuss the project in more detail and confirm eligibility. A copy of the project specific participant information sheet (PIS) will be provided. In all cases, potential participants will be given written information and the opportunity to discuss the project with one of the research team prior to recruitment.

### 5.1.4 Consent Visit (Visit 1) – Duration <1 hour

To facilitate recruitment participants will be offered home and/or evening visits where this can be supported by the recruiting site.

Following written informed consent demographic and clinical features will be recorded, including weight, height, waist/hip ratio & blood pressure. Data will be collected relating to the patient's diabetes, diagnosis and other relevant medical condition and will include a hypoglycaemia questionnaire. Non-fasting (within 1-5 hours of a meal) blood sample will be collected at all sites for

- Serum C-peptide and other routine biochemistry
- Islet autoantibodies (GAD, IA2, ZnT8)
- DNA extraction (T1D genetic risk score typing, biobanking)
- Plasma and serum samples for storage for future analysis

At selected sites, blood sample will also be collected for additional tests including immune function analysis

Total blood sample volume to be collected at visit 1 will be  $\leq 90$ ml (volume in sites not undertaking immune function studies  $\leq 40$ ml).

Samples will be transferred to Exeter Clinical Laboratory (Royal Devon and Exeter NHS Foundation Trust) directly by post or frozen for subsequent batched transfer.

Participants will be given sterile collection kits and prepaid packaging for home post meal urine or capillary blood collection. The sample will be posted directly to Exeter Clinical laboratory and will be analysed for Urinary C-Peptide Creatinine Ratio (UCPCR) or serum C-peptide

Samples will be collected and processed in accordance with detailed SOPs.

Islet autoantibody results (with clinical interpretation) will be reported to clinicians and participants within 4 weeks of visit 1.

With specific consent additional data will be collected from clinical and laboratory records including diagnosis weight, HbA1c, FBC, glucose and lipid profile, and confirmation of ketoacidosis.

Participants will be asked to complete an optional 25 question questionnaire assessing psychological wellbeing and resilience (31, 32).

At some sites, participants will be offered the option to gift samples taken during their routine diabetes care to be used to aid the on-going collection of research data (e.g. biochemical analysis for indicators of long-term insulin production).

### 5.1.5 Follow-Up - Visits 2 & 3

**Follow up by telephone, email, post or in person at 1 year (10-16 months) and 2 years (22-28 months)**

Duration: <15 minutes

At approximately 1 year and 2 years post recruitment, participants will be contacted to record concurrent treatment, hypoglycaemia and health service utilisation.

Participants will be asked to collect a home post meal urine or capillary blood sample and post to the Exeter Clinical Laboratory for Urinary C-Peptide /Creatinine Ratio (UCPCR) or serum C-peptide

HbA1c results will be obtained from participants GP practice or laboratory records.

**5.1.6 Follow Up - Visit 4****Follow up visit at 3 years (34-40 months)**

Approximate duration: 30 minutes

Participants will be invited to attend a further face to face non-fasting visit.

Weight, blood pressure, concurrent treatment, hypoglycaemia and health service utilisation will be recorded.

Participants will be asked to complete a further, optional, wellbeing/resilience questionnaire.

A non-fasting (ideally within 1-5 hours of a meal) blood sample will be collected at all sites for

- Serum C-peptide and other routine biochemistry
- Plasma and serum samples for storage for future analysis

At selected sites, blood sample will also be collected for additional tests including immune function analysis.

Total blood sample volume to be collected at visit 4 will be  $\leq 85$ ml (sites without immune function tests  $\leq 35$ ml)

**5.1.7 Clinical Reporting**

With specific consent from the participant, results of assays of clinical relevance (including routine clinical bloods analysed at local site, baseline autoantibodies and C-peptide assessment at 3 years) will be copied to the participant's GP or secondary care clinician with information on test interpretation.

Baseline islet autoantibody results and 3 year C-peptide will be sent to participants, with patient appropriate information on interpretation, from the central research team at the lead site.

## **6. WITHDRAWAL & END OF STUDY**

### **6.1 Withdrawal criteria**

Subjects will be informed that they are free to withdraw from the study at any time up until the samples and data are coded but not anonymised. When samples are fully anonymised, the participants will still be able to withdraw but their samples and associated data will be retained for use in analysis. If a patient permanently withdraws from the study, or is lost to follow-up, the reason will be recorded.

Criteria for discontinuing participation in the study are:

- Participant withdrawal of consent.
- Investigator's discretion that it is in the best interest of the participant to withdraw.
- Termination of the study by the sponsor or funding body.

### **6.2 End of Study**

We will recruit participants over 30-36 months, with 36 months participant follow up (total duration of study = 66-72 months. Individual participant involvement = 36 months). The study will end when the last participant has completed the study. The study may be discontinued at the sponsor's or CI's discretion.

## **7. SAMPLE PROCESSING**

The sample processing procedures described below will be conducted in accordance with detailed SOPs provided to all sites by the CI.

### **7.1 Sample Transfer & Initial Analysis**

Following sample collection, initial analysis may be undertaken locally or centrally, depending on the best logistical method that optimises sample analysis accuracy (this may differ for different biomarkers, some being more stable than others).

At each study visit blood and/or urine samples will be transferred to the Royal Devon & Exeter NHS Foundation Trust Blood Sciences Laboratory for central analysis and biobanking according to detailed sample handling SOPs.

Samples transferred to the Exeter blood sciences laboratory for analysis will be labelled with participant identifiable data (Name, date of birth & NHS number) in accordance with the requirements for clinical sample analysis. Once initial analysis is complete, the remaining samples will be anonymised and assigned an individual study code prior to storage.

DNA will be extracted by the Royal Devon and Exeter Hospital Clinical Genetics Laboratory who will store extracted DNA pending analysis. Blood samples for DNA extraction will be labelled with the study name and unique study code but not patient identifiable data.

### **7.2 Sample Storage Procedures**

All saved serum, plasma and DNA samples will be stored under a unique ID code, with the file linking the code to personal identifiable information held securely by the CI and appropriate local PI and accessible only to personnel with training in data protection who require this information to perform their duties.

### **7.3 Long Term Storage & Future Analysis**

Enduring consent will be sought to store the samples (serum, plasma and DNA) in the Peninsula Research Bank (PRB) following completion of analysis for this study. All future analysis of samples and/or data will be conducted with the specific agreement of the PRB steering committee.

## **8. DATA COLLECTION AND RECORDING**

### **8.1 Data Collection Form**

Data will be obtained and recorded on a paper data collection form (DCF) with all forms returned to the NIHR Exeter Clinical Research Facility and entered onto a specially designed database. Data collected on the DCFs and subsequently entered onto the database will be reviewed for discrepancies, missing data and queries.

### **8.2 Source Data**

CVs, delegations logs, DCFs and questionnaires will be deemed source data.

### **8.3 Data Monitoring**

The coordinating research team will undertake regular audits of raw data for both accuracy and completeness and research data will be cleaned before analysis is undertaken. The CI reserves the right to close recruiting sites who fail to meet data and sample quality standards on a regular basis.

### **8.4 Data Confidentiality**

All participant data will be held in a link-anonymised format, with personal identifiable data only accessible to personnel with training in data protection who require this information to perform their duties. Participants' research and sample data will be identified by unique study ID numbers and all data will be held on password-protected computers. All paper copies of study data will be stored under ID number and kept in locked offices within the research facilities. Researchers involved in data and sample analysis will not have access to personal identifiable data.

### **8.5 Data Storage and Archiving**

All consent and data collection forms will be held in the relevant local research centre, with access to personal identifiable data restricted to personnel with training in data protection who require this information to perform their duties. Where consent and data collection forms are completed at primary/secondary care or home locations, these forms will be sent to the research centre for monitoring and data entry. The coordinating research team will undertake regular audits of raw data for both accuracy and completeness and research data will be cleaned before analysis is undertaken.

At the end of the study, archiving at each recruitment site will be carried out in accordance with local policy.

At the end of the study, following analysis, anonymised data (together with samples) will be transferred to the Peninsula Research Bank for long term storage and management.

## 9 STATISTICS AND DATA ANALYSIS

### 9.1 Sample Size

#### *Diagnosis <= age 50 cohort*

Assuming conservative estimates that 25% of participants will have Type 1 diabetes (18) and 80% of participants will have the primary outcome measure a sample size of 1000 (<50 cohort) will give confidence intervals of 85-94% and 87-92% around a biomarker sensitivity/specificity of 90% for Type 1 diabetes (33).

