## STUDY SUMMARY

StudyTitle	STARTRIGHT: Getting the right classification and treatment from diagnosis in adults with diabetes
Internal ref. no. (or short title)	CRF243 (StartRight Study)
Study Design	Prospective observational
Study Participants	Adults who have been diagnosed with diabetes (excluding gestational or secondary diabetes) for $\leq 1$ year at the time of study recruitment. Aged $\geq 18$ at the time of diabetes diagnosis.
Planned Sample Size	Main cohort: 1000 Additional late onset diabetes cohort: 800
Follow up duration	3 years
Planned Study Period	6 years
Study Summary	This study aims to achieve more accurate early classification of diabetes and identification of which patients will rapidly require insulin treatment. We will recruit 1200 participants who have been diagnosed with diabetes in the last year and were aged between 18 and 50 years at the time of diagnosis. We will recruit an additional cohort of 800 participants diagnosed after age 50. We will record clinical features and biomarkers that may help us to determine diabetes type at diagnosis and follow participants for 3 years to assess the development of severe insulin deficiency (measured using C-peptide) and insulin requirement. We will assess utility of clinical features and additional biomarkers in identifying patients with rapid progression to insulin requirement. Findings will be integrated into a freely available clinical prediction model.

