## STUDY PROTOCOL

**StartRight: Getting the right classification and treatment from diagnosis in adults with diabetes.**

### 1 Lay summary

The treatment of Type 1 and Type 2 diabetes is very different. People with Type 1 diabetes rapidly stop making their own insulin, so need insulin injections from diagnosis. People with Type 2 diabetes can keep making their own insulin but it may not work as well as it should, so they can be treated with diet or tablets. While they may eventually need insulin treatment it is usually not until many years after diagnosis.

It is often difficult for doctors to tell which kind of diabetes a person has. Because of this, sometimes people are given the wrong diagnosis. This can have a huge impact as it means they could receive the wrong treatment. A person incorrectly diagnosed with Type 1 diabetes will be prescribed unnecessary insulin injections and miss out on other helpful therapies. A person incorrectly diagnosed with Type 2 diabetes may develop severely high glucose and become unwell with a condition called Diabetic Ketoacidosis if they do not receive insulin treatment.

This study aims to improve this situation by helping doctors more accurately tell the type of diabetes a person has when they are first diagnosed. We will recruit 1000 participants who have recently been diagnosed with diabetes between the ages of 18 and 50. We will recruit an additional 800 recently diagnosed participants who developed diabetes after age 50, half of whom will be receiving insulin therapy. We will record clinical features and measure blood tests that may help us determine diabetes type at diagnosis and follow participants for 3 years to see whether they stop producing their own insulin and need insulin treatment, which confirms Type 1 diabetes. We will assess whether clinical features and blood tests can help us tell if a patient needs rapid insulin treatment and should be initially treated as Type 1 or Type 2 diabetes.

We will combine results from this study and existing previous studies to produce a calculator, called a clinical probability model that will allow doctors and patients to combine information from clinical features and (where necessary) blood tests to accurately diagnose what type of diabetes a person has and therefore give the correct treatment. This will be freely available to doctors and patients as a website calculator and smartphone app.

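### The 18-50 cohort is given as both 1000 and 1200; section 9.1 still plans for 1000 at 25% Type 1, and the 200 added insulin-treated recruits are not reflected in the planning prevalence or the incidence adjustment

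*Protocol*

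**What the plan says.** The current protocol text gives the size of the 18-50 cohort five times, with two values.

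- Study Summary, planned sample size row: "Main cohort: 1000 Additional late onset diabetes cohort: 800".
- Study Summary, narrative row of the same table: "We will recruit 1200 participants who have been diagnosed with diabetes in the last year and were aged between 18 and 50 years".
- Section 1, Lay summary: "We will recruit 1000 participants who have recently been diagnosed with diabetes between the ages of 18 and 50".
- Section 4, Study Design: "We will recruit a prospective cohort of 1200 adults diagnosed with diabetes within the previous 1 year".
- Section 9.1: "a sample size of 1000 (<50 cohort) will give confidence intervals of 85-94% and 87-92" per cent, around an accuracy of 90%. The inputs are a Type 1 share of 25%, labelled conservative, and the assumption that "80% of participants will have the primary outcome measure".

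The amendment schedule in section 16 explains where 1200 comes from. SA03 adds 200 people on insulin whose diabetes was diagnosed after age 30, brings the cohort to 1200, and closes recruitment of anyone else to it. Sections 4, 4.3.1 and 5.1.2 do not describe this restriction for the younger cohort. Section 5.1.2 describes targeting by insulin status only for those over 50.

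Section 9.3 analyses the two age groups separately. It plans to adjust model predictions to population incidence of Type 1 diabetes for the over-50 cohort, and mentions no such step for the younger one.

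**The concern.** A planned sample size should have one value, and the precision statement should belong to the cohort that is being recruited. Here the Study Summary disagrees with itself, and section 9.1 describes a cohort that section 4 has replaced.

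The second issue is case mix. The added 200 were selected on insulin treatment, and the protocol treats that as a marker of high Type 1 prevalence when it explains the over-50 recruitment (section 5.1.2). The same kind of enrichment in the younger cohort would raise its Type 1 share above 25%. The main product is a probability calculator for clinicians and patients. A model fitted to an enriched cohort and not adjusted would tend to predict probabilities that are too high for the population in which it is used.

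**Working it through.** **Inputs.** From section 9.1: cohort 1000, Type 1 share 25%, outcome available in 80%, sensitivity and specificity 90%. From section 4: cohort 1200. From SA03: the extra 200 are insulin treated. The confidence level is not stated; I assume 95%, two-sided.

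The protocol gives no Type 1 share for insulin-treated people diagnosed at 31-50. I take an assumed range from two of its other figures:

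- 48%, the share in section 9.1 for people over 50 who were insulin treated within 12 months of diagnosis;
- 74% = 100% − 26%, where 26% is the misclassification figure in section 2 for people treated with insulin from diagnosis.

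**Step 1: reproduce the plan.**

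Type 1 with outcome = 1000 × 0.80 × 0.25 = 200. Type 2 with outcome = 1000 × 0.80 × 0.75 = 600.

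The exact (Clopper-Pearson) limits for x successes in n are the 2.5% quantile of Beta(x, n−x+1) and the 97.5% quantile of Beta(x+1, n−x). With 180/200 and 540/600 they are 85.0-93.8% and 87.3-92.3%. These round to the stated figures.

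**Step 2: change only the size to 1200.**

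Type 1 = 1200 × 0.80 × 0.25 = 240. Type 2 = 720. The limits are 85.5-93.5% and 87.6-92.1%.

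**Step 3: 1000 at 25% plus 200 at share q.**

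Overall share = (250 + 200q)/1200. Type 1 with outcome = 0.80 × (250 + 200q). Type 2 with outcome = 0.80 × (950 − 200q).

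- q = 0.48: share 346/1200 = 28.8%; counts 276.8 and 683.2, rounded to 277 and 683.
- q = 0.74: share 398/1200 = 33.2%; counts 318.4 and 641.6, rounded to 318 and 642.

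| Scenario | Type 1 / Type 2 with outcome | Sensitivity | Specificity |
|---|---|---|---|
| 1000, 25% (plan) | 200 / 600 | 85.0-93.8% | 87.3-92.3% |
| 1200, 25% | 240 / 720 | 85.5-93.5% | 87.6-92.1% |
| 1000 + 200, q = 0.48 | 277 / 683 | 85.7-93.2% | 87.5-92.2% |
| 1000 + 200, q = 0.74 | 318 / 642 | 86.1-93.0% | 87.5-92.2% |

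In the last two rows 90% of the count is not a whole number, so successes were rounded to the nearest one. No limit moves by more than about 1.1 points from the plan, and every interval is narrower.

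**Step 4: effect on predictive value.**

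PPV = 0.9p / (0.9p + 0.1(1 − p)), where p is the Type 1 share.

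- p = 0.25: 0.225/(0.225 + 0.075) = 75.0%.
- p = 0.288: 0.2595/(0.2595 + 0.0712) = 78.5%.
- p = 0.332: 0.2985/(0.2985 + 0.0668) = 81.7%.

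This rise comes from recruitment alone, since test accuracy is held fixed.

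**The case against.** A reader might infer that the intervals in section 9.1 are miscalculated or that the cohort is too small. Neither holds. The intervals are right for the inputs they state, and moving to 1200 only narrows them. A calculation described as conservative can also tolerate a larger cohort and a higher Type 1 share.

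The case-mix part is less firm than the contradiction in size, for four reasons.

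- Who the extra 200 are appears only in the amendment schedule. That entry agrees with the 1200 in section 4 and is the only explanation of it, so I rely on it, but the design sections do not repeat it.
- Both proxies are imperfect. The 48% comes from people over 50. The 26% stands in a sentence that also refers to diagnosis before age 35, and it concerns insulin from diagnosis, whereas SA03 refers to people receiving insulin. A reader might settle on 33% and 82% as the result, but those come from the higher proxy alone.
- The primary objective concerns diagnostic performance, and section 9.1 plans for sensitivity and specificity. No predictive-value target is set.
- Details such as a recruitment-phase flag or intercept recalibration could sit in a statistical analysis plan that is not shown.

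These points limit the size of the claim but do not remove it. The 1000/1200 conflict lies wholly in current text. The planned outputs include predicted probabilities, and section 9.3 itself names the incidence adjustment for one cohort only. The overall share stays at 25% only if insulin-treated recruits have no more Type 1 diabetes than the rest, which is hard to square with the protocol's own 48% against 3.9% by insulin status in the over-50s.

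**Conclusion.** The planned size of the 18-50 cohort contradicts itself, and section 9.1 was not updated to the 1200 in section 4. That is certain from the text. Its effect on precision is small and favourable: limits shift by about one point or less, up to 1.1 at the top of the assumed range.

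The case-mix shift is conditional. It assumes that SA03 describes the added 200 correctly, that the other 1000 have 25% Type 1, that outcome availability is 80% in both groups, and that 48-74% of the added recruits have Type 1 diabetes. Under these assumptions the overall share is about 29-33% and the positive predictive value 78-82% instead of 75%. As section 9.3 stands, the younger model would carry that shift in its predicted probabilities.

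It would also be tempting to treat the other 1000 as an unselected sample and take prevalence from them. The protocol does not support this: section 5.1.1 allows self-referral, research databases, and sites that recruit only from primary or only from secondary care.

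**What to change.** 1. State 1200 for the 18-50 cohort in the Study Summary sample-size row, the lay summary and section 9.1, to match section 4 and the summary narrative.
2. Describe in section 4 the 200 insulin-treated recruits diagnosed after age 30.
3. Redo the 9.1 precision statement for 1000 plus 200, with the mixed Type 1 share shown as a range and its source given. State the confidence level and the interval method.
4. In section 9.3, extend the population-incidence adjustment to the model for those diagnosed at 50 or younger, and flag the SA03 recruits in the dataset so that the adjustment can take account of how they were selected. Use an external incidence source for this age group, and do not use the other 1000 as a stand-in for the population.

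The cost is protocol wording, a short recalculation and a little more analysis. No further participants or procedures are needed.
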